3.2.3. Treatment Groups

There is only one treatment group EN3835 1.68 mg total dose (0.84 mg per treatment area) in this study.

3.2.4. Protocol Deviations

A listing of protocol deviations will be provided. Before database lock, the statistical team will programmatically check against the prespecified criteria provided in a separate document ie, Protocol Deviation Checklist, and produce a subject list outputs under each criteria. The data review team will review the outputs and the protocol deviation tracker obtained during the study conduct, and then determine the major/minor category for each deviation. If any data points or subjects are excluded from the analysis, they will be documented in the data review meeting minutes and also be presented in a data listing.

3.2.5. Effectiveness Parameters

3.2.5.1. Baseline CR-PCSS Score

Baseline CR-PCSS scores for the assigned region will be based on the investigator's CR-PCSS evaluation done at the Screening visit.

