Study Design: This study is a Phase 2, open-label study of safety and effectiveness of EN3835 in the treatment of EFP in adult women. Subjects will be screened for study eligibility within 14 days prior to enrolling in this study. Subjects with at least 2 bilateral treatment areas (bilateral buttocks or bilateral posterolateral thighs) (also referred to as a region) (eg, their left and right buttocks or left and right posterolateral thighs) with mild, moderate or severe levels of cellulite as assessed by the Investigator using the Clinician Reported Photonumeric Cellulite Severity Scale (CR-PCSS) and a Hexsel Cellulite Severity Scale no greater than 13 will be eligible. If both their left and right buttocks AND left and right posterolateral thighs are eligible, one pair will be randomly selected as the assigned treatment areas. Subjects will receive an open-label treatment course which consists of up to 3 treatment visits (ie, Day1, Day 22, and Day 43). Each treatment visit will consist of 12 injections (0.3 mL per injection of EN3835 0.07 mg/injection) in each of the treatment areas of the region for a total volume of 7.2 mL (1.68 mg). Selection of dimples to be treated in the assigned treatment areas will be at the discretion of the Investigator. End-of-study will occur at study Day 180. At each treatment visit, the Investigator will first conduct a live assessment of each treatment area of the assigned region using the CR-PCSS. The Investigator will then select and mark the dimples to be treated within each treatment area. All the assessments must be done before marking the dimples for injection. At Day 180 (End of Study/Early Termination), The Investigator will conduct live assessments of each of the treatment area using the CR-PCSS. The subject will complete the Subject Satisfaction with Cellulite Treatment assessment. In a photographic sub-study at two sites, subjects will return to the site to have their treated areas photographed at 1, 3, 6, and 13 days after each treatment visit to assess local site reactions post-injection.	
Number of Subjects (planned): Up to 150	
Study Center(s): Approximately 10 sites in United States	

Name of Sponsor/Company: Endo Pharmaceuticals Inc.
Name of Investigational Product: EN3835
Name of Active Ingredient: Collagenase clostridium histolyticum

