
Investigational Product, Dosage and Mode of Administration: EN3835, 1.68 mg, subcutaneous. A dose of 0.84 mg of EN3835 per treatment area will be administered as 12 subcutaneous injections (0.3-mL injection administered as three 0.1-mL aliquots per injection) in each of two treatment areas for a total dose of 1.68 mg and a total volume of 7.2 mL (3.6 mL per treatment area). Total number of injections will be 24 injections per treatment visit into the assigned region (left and right buttocks or left and right posterolateral thighs). There will be 3 treatment visits at 21-day intervals, ie, treatments on Days 1, 22, and 43 will be administered.

Duration of Study: Up to 194 days (includes screening phase)
 
Screening Phase: Up to 14 days

Name of Sponsor/Company: Endo Pharmaceuticals Inc.
Name of Investigational Product: EN3835
Name of Active Ingredient: Collagenase clostridium histolyticum

Criteria for Evaluation:
 
Safety:
 
Safety will be assessed throughout the study through the recording of:
 
 • Adverse events (AEs) (including those of special interest (AESI); which are adverse events such as [REDACTED]) • Vital signs • Clinical laboratory tests • Immunogenicity assessment (ie, assessed through the determination of binding and neutralizing anti-AUX-I and anti-AUX-II antibody levels) 
In addition, injection site reactions/local tolerability in the treated areas (through subject and Investigator reporting) will be assessed.
 
Effectiveness:
 
 • Investigator using the CR-PCSS by live assessment: 5-level scale ranging from 0 (no cellulite) to 4 (severe cellulite) (Day 1 (Baseline) and Days 22, 43, 90, and 180) for each treatment area • Subject satisfaction with cellulite treatment assessment: 5-level scale ranging from 2 (very satisfied) to -2 (very dissatisfied) (Day 180)

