13. ASSESSMENT OF EFFECTIVENESS

13.1. Effectiveness Measurements

13.1.1. Clinician-Reported Photonumeric Cellulite Severity Scale (CR-PCSS)

The CR-PCSS will be conducted for the purpose of assessing the severity of cellulite in the buttock or thigh; there are separate scales for buttocks or thighs. The scales are 5-level photonumeric scales developed specifically for clinicians and used by the Investigator to assess the severity of the subject's cellulite in each treatment area by live assessments; the ratings range from 0 (None) to 4 (Severe) with labels and descriptors to aid the Investigator in the assessments.

Investigators will be trained and qualified on the use of the CR-PCSS prior to assessing any subjects.

At the Screening visit, the Investigator will determine severity of cellulite of each of the 4 treatment areas by assessing subjects using the CR-PCSS for buttock ([Appendix B](#)) or thigh ([Appendix C](#)). Before injections on treatment visits Day 1, Day 22, and Day 43, and on visit Day 90 and Day 180, Investigators will evaluate each of the two assigned treatment areas via live assessment. If the buttocks are the treated region, the Investigator will use the CR-PCSS for the buttock to make his/her evaluation; if the thighs are the treated region, the Investigator will use the CR-PCSS for the thigh to make his/her evaluation.

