3.1.4. Clinician Reported Photonumeric Cellulite Severity Scale (CR-PCSS)

The CR-PCSS will be conducted for the purpose of assessing the severity of cellulite in the buttock or thigh; there are separate scales for buttocks or thighs. The scales are 5-level photonumeric scales developed specifically for clinicians and used by the Investigator to assess the severity of the subject's cellulite in each treatment area by live assessments; the ratings range from 0 (None) to 4 (Severe) with labels and descriptors to aid the Investigator in the assessments.

The Investigator will determine severity of cellulite of each of the 4 treatment areas at the Screening visit, and evaluate each of the two assigned treatment areas before injections on treatment visits Day 1, Day 22, and Day 43, and on visit Day 90 and Day 180 (EOS/ET) using the CR-PCSS. If the buttocks are the treated region, the Investigator will use the CR-PCSS for the buttock to make his/her evaluation; if the thighs are the treated region, the Investigator will use the CR-PCSS for the thigh to make his/her evaluation.

The following labels and descriptions are associated with each level of severity on the CR-PCSS Buttock scale:

- 0: None: No dimples or evident cellulite
- 1: Almost None: Few dimples that are mostly superficial in depth
- 2: Mild: Several dimples of which most are shallow in depth
- 3: Moderate: Many dimples of which most are moderate in depth
- 4: Severe: A lot of dimples with some of more severe depth

The following labels and descriptions are associated with each level of severity on the CR-PCSS Thigh scale:

- 0: None: No depressions or raised areas
- 1: Almost None: A few depressions or undulations that are mostly superficial in depth
- 2: Mild: Several undulations that are shallow in depth with areas of slight protuberances

- 3: Moderate: Many undulations with alternating areas of protuberances and depressions, of which most are moderate in depth
- 4: Severe: A lot of undulations with alternating areas of protuberances and depressions, some of more severe depth

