3.4.5. EFP Baseline Severity

EFP baseline severity variable characteristics (including CR-PCSS rating and Hexsel CSS total score from Screening Visit) will be summarized by assigned region (buttock or thigh) and overall in the safety population.

Individual subject listing of all Hexsel CSS results will be generated.

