3.4.6.1. CR-PCSS

3.4.6.1.1. CR-PCSS Rating Summaries

The investigator CR-PCSS ratings will be summarized by assigned region (buttock or thigh) and overall at baseline (prior to Day 1), Day 22, Day 43, Day 90, and Day 180 (EOS/ET) with counts and percentages at each severity rating and with means and standard deviation. The change from baseline in CR-PCSS score will be summarized by assigned region (buttock or thigh) and overall at Day 22, Day 43, Day 90, and Day 180 (EOS/ET) with counts at each change score and with means and standard deviation. The change from baseline score can vary from -4 (change from severe to none) to +2 (change from mild to severe).

Individual subject listing of CR-PCSS ratings will be generated.

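### The SAP measures CR-PCSS change from the Screening rating that also decides entry, while other sections require a Day 1 pre-injection rating that the visit schedules omit

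*SAP*

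**What the plan says.** **Screening as baseline.** SAP 3.2.5.1 bases the score on the "CR-PCSS evaluation done at the Screening visit". SAP 3.4.5 describes baseline severity as "including CR-PCSS rating and Hexsel CSS total score from Screening Visit". SAP 3.4.6.1.1 summarises ratings "at baseline (prior to Day 1), Day 22, Day 43, Day 90, and Day 180 (EOS/ET") and adds: "The change from baseline score can vary from -4 (change from severe to none) to +2 (change from mild to severe").

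**A Day 1 rating required.** Protocol 13.1.1: "Before injections on treatment visits Day 1, Day 22, and Day 43, and on visit Day 90 and Day 180, Investigators will evaluate" each assigned area. SAP 3.1.4 has the investigator "evaluate each of the two assigned treatment areas before injections on treatment visits Day 1, Day 22, and Day 43". The protocol synopsis and SAP 3.1 both state: "At each treatment visit, the Investigator will first conduct a live assessment of each treatment area of the assigned region using the CR-PCSS". The synopsis list of effectiveness measures gives the CR-PCSS times as "Day 1 (Baseline) and Days 22, 43, 90, and 180) for each treatment area".

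**No Day 1 rating shown.** The CR-PCSS row of the Schedule of Events (protocol section 5 and SAP Table 1) is marked at Screening, Day 22, Day 43, Day 90 and Day 180, with the Day 1 cell empty. The Day 1 pre-injection list in protocol 12.3.1 has no CR-PCSS step, whereas the matching list for Days 22 and 43 (12.5.1) has one.

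**Entry gates.** Protocol 11.1 and 12.1.2.3 require a Screening CR-PCSS of at least 2 and a Hexsel CSS of at most 13 in each area. Hexsel is scored straight after CR-PCSS (12.1.2.2). Schedule footnote d and protocol 13.1.3 call for Hexsel again on Day 1; the Schedule rows and SAP 3.1.6 show it at Screening only, and 12.3.1 omits it.

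**The concern.** Two things are at issue. First, the documents disagree on whether a Day 1 CR-PCSS exists and on which score is the baseline. A site working from the Schedule and 12.3.1 would skip a rating that 13.1.1 requires, and it cannot be recovered later. Protocol 17.5.1 does not define baseline for effectiveness, and the last-value-before-first-dose rule in 17.6 covers safety parameters only.

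Second, the score that selects an area is also the reference for its change and responder status. Areas whose true severity lies near the cut-off enter more often when Screening error pushes the score up, and later ratings then fall back without any treatment effect. The Hexsel cap can act the other way: if the two scales share error at the same visit, it removes areas whose Screening ratings ran high. The study has a single arm, so nothing cancels either artefact, and the change scores and the 1-level and 2-level responder rates are the clinician-rated effectiveness results.

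**Working it through.** **1. The plan's own figure.** The stated range of change is the one figure that depends on the baseline. Change = later score minus baseline.
- Gated Screening baseline (2, 3 or 4), later score 0 to 4: minimum 0 − 4 = −4, maximum 4 − 2 = +2. This matches SAP 3.4.6.1.1 exactly.
- Ungated Day 1 baseline (0 to 4): minimum −4, maximum 4 − 0 = +4, or 4 − 1 = +3 if areas rated 0 on Day 1 are left out.

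The printed range therefore holds only for the gated Screening score.

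**2. Simulation with no treatment effect.** The gates come from the protocol; everything else is assumed.
- Rating = latent severity + persistent error + visit error, rounded and clipped to 0–4.
- Latent mean 1.5, 2.0, 2.5 or 3.0; latent SD 0.8 or 1.0; left/right latent correlation 0.8.
- Reliability r of 0.6, 0.7, 0.8 or 0.9, with error variance = SD² × (1 − r)/r.
- Share of error variance that persists across visits: 0, 50% or 100%.
- Both areas at least 2 at Screening; 400,000 simulated subjects per scenario before gating.

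This gives 4 × 2 × 4 = 32 settings at each persistence level, so 64 with persistence of 0 or 50%.

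**3. Central example** (mean 2.0, SD 0.8, r = 0.8, so error variance 0.64 × 0.2/0.8 = 0.16):

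| Persistent share of error | 1-level rate, Screening baseline | 1-level rate, Day 1 baseline | Difference |
|---|---|---|---|
| 0 | 24.8% | 21.5% | 3.3 points |
| 50% | 18.2% | 15.5% | 2.7 points |
| 100% | no difference | no difference | 0 |

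The 2-level rates with independent error are 1.0% and 0.8%.

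**4. CR-PCSS gate alone, 64 scenarios** (Screening minus Day 1 baseline):
- 1-level rate: 0.4 to 10.9 points, median 2.7. Medians at latent means 1.5, 2.0, 2.5 and 3.0 are 6.1, 3.8, 2.1 and 1.0.
- 2-level rate: 0 to 4.6 points, median 0.17, and below 1 point in 53 of 64.

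Repeating steps 3 and 4 with another seed moves these results by a few tenths of a point at most (and the 53 to 54).

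**5. Hexsel cap added at Screening.** Hexsel is assumed to be 3.75 × (latent + error), rounded and clipped to 0–15, because 15/4 = 3.75 maps one scale onto the other. Difference in the 1-level rate:

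| Error shared with CR-PCSS | Range (points) | Median | Negative in |
|---|---|---|---|
| None | 0.5 to 12.9 | – | 0 of 64 |
| Half | −1.5 to 10.4 | 2.1 | 11 of 64, all at mean 3.0 |
| All | −4.4 to 8.9 | 0.9 | 28 of 64, at means 2.5 and 3.0 |

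**6. Hexsel cap also applied on Day 1.** The Day 1 baseline then carries its own spurious mean change: 0.00 to +0.12 level with half the error shared, up to +0.19 with all of it. It remains smaller in absolute size than the Screening artefact in 55 (half shared) and 46 (all shared) of 64 scenarios. The exceptions are all at means 2.5 and 3.0.

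**7. Other assumptions.** With observed SD 0.8, latent means up to 3.5 and reliability down to 0.5, the 1-level difference runs from 40.1% − 27.9% = +12.2 points (CR-PCSS gate alone) to 20.0% − 26.5% = −6.5 points (Hexsel cap, error correlation 0.8). The ranges in steps 4 and 5 are therefore not bounds.

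**8. Low Day 1 scores.** Under the CR-PCSS gate with 0 or 50% persistence, 0.8% to 22.5% of areas (median 6.5%) and 1.6% to 37.2% of subjects (median 11.9%) have a Day 1 score below 2; 0% to 8.7% of subjects (median 0.2%) have an area at 0. All are 0% under full persistence.

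**The case against.** The SAP's rule is explicit and consistent within itself: 3.2.5.1, 3.4.5, 3.4.6.1.1 and the stated range all point to Screening, so an analyst would not be in doubt. Most passages that require a Day 1 rating do not call it the baseline; only the synopsis list does. A pre-injection rating also has another use, because protocol 12.2 ties injection to an area not scoring 0. Effectiveness is secondary and descriptive, with no test or threshold. The central gap of 3.3 points is about half the sampling uncertainty: with 150 evaluable subjects and one area each, the 95% half-width is 1.96 × √(0.248 × 0.752/150) = 6.9 points at 24.8%, and 6.6 points at 21.5%. Nor is Day 1 always the less biased choice: if Hexsel is confirmed that day, it fails to be so in 64 − 55 = 9 or 64 − 46 = 18 of 64 scenarios.

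These points limit the weight and are accepted as such. They do not remove the problem. A clear SAP rule still contradicts the synopsis, and no passage says how the required Day 1 rating enters the effectiveness analysis. The schedules may prevent it from being collected at all. Bias, unlike sampling error, does not shrink with more subjects, and an uncertain sign is a reason to show both results.

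**Conclusion.** The concern holds. The textual conflict is certain: the protocol contradicts itself on whether Day 1 is rated, the SAP does the same, and the SAP's baseline differs from the one named in the synopsis. The effect on results is possible but not measurable from the documents. The CR-PCSS gate alone pushes towards apparent improvement unless rating error fully persists between visits; the Hexsel cap can cancel or reverse that when severity is high and the two scales share error. The likely size is a few points on the 1-level rate and usually under one point on the 2-level rate, conditional on the assumed severity, reliability, persistence and Hexsel mapping. A Day 1 baseline removes only the bias from the CR-PCSS gate. Any Day 1 Hexsel selection, chance responders and open-label rating bias would remain. This should be corrected, but it does not affect the safety objective or the sample size.

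**What to change.** 1. Mark CR-PCSS on Day 1 before injection in both Schedules of Events, and add it to protocol 12.3.1 ahead of dimple marking.
2. In SAP 3.2.5.1, define baseline as the Day 1 pre-injection score of each assigned area. Use Screening only where Day 1 is missing, and report how often, because the fallback mixes gated and ungated scores.
3. Align SAP 3.4.5 and 3.4.6.1.1: drop the wording that places baseline before Day 1, and give the range as −4 to +4, or −4 to +3 if areas at 0 on Day 1 are excluded.
4. Keep Screening for eligibility, and show change and responder rates from the Screening baseline as a sensitivity summary.
5. Report how many areas score 1 and how many score 0 on Day 1. Neither can be a 2-level responder, and an area at 0 cannot be a 1-level responder.
6. Reconcile a possible Day 1 score of 0 with the text of protocol 12.2. No clinical rule is proposed here.
7. State whether the Day 1 Hexsel confirmation is performed, align SAP 3.1.6 and 12.3.1 accordingly, and say that a Day 1 baseline removes only the CR-PCSS-gate bias.

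If Day 1 ratings were not collected, keep Screening and state the possible bias beside the change-score and responder tables.

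**Cost.** SAP edits to 3.2.5.1, 3.4.5, 3.4.6.1.1 and Table 1, with consequential changes to 3.1.6, 3.4.6.1.2 and the table shells. Protocol section 5 and 12.3.1 (and 12.2 if its text changes) need an amendment with IRB approval. Responder rates may come out lower or, in a severe population with shared rating error, higher.

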3.2.5.2. Change from Baseline in CR-PCSS Score

The change from baseline in CR-PCSS score will be the CR-PCSS score at each visit minus the baseline score. The more negative the change from baseline indicates a greater improvement of cellulite severity in the assigned region.

3.2.5.3. Clinician Responder

A 2-level clinician responder for a treatment area is defined as a subject with an improvement in the CR-PCSS rating of at least 2 levels from baseline (ie, change from baseline in CR-PCSS rating of -2, -3, or -4) on that treatment area. A 1-level clinician responder for a treatment area is defined as a subject with an improvement in the CR-PCSS rating of at least 1 level from baseline (ie, change from baseline in CR-PCSS rating of -1, -2, -3, or -4) on that treatment area.

3.2.5.4. Subject Satisfaction with Cellulite Treatment

The subject satisfaction response is one of the five ratings (+2, +1, 0, -1, and -2) for the region treated, assessed at visit Day 180 (EOS/ET).

3.2.6. Safety Parameters

3.2.6.1. Adverse Events

Adverse events will be mapped to preferred term using the Medical Dictionary for Regulatory Activities (MedDRA), Version 19.0. Treatment-emergent AEs are any AEs with a start date equal to or after the date of the first injection. Treatment-related AEs are any AEs with a relationship of possibly or probably related to study medication or AEs with a missing relationship.

3.2.6.1.1. Adverse Event Treatment Session

An AE's association with a treatment session will be based on the start date of AEs compared to the date of the injection. Adverse events with a start date between the Day 1 visit date and the day prior to the Day 22 visit date will be associated with Treatment Session 1. AEs with a start date between the Day 22 visit date and the day prior to the Day 43 visit date will be associated with Treatment Session 2. AEs with a start date between the Day 43 visit date and the Day 180 (EOS/ET) visit date will be associated with Treatment Session 3.

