10. INVESTIGATIONAL PLAN

10.1. Study Design

This study will be performed at approximately 10 study centers located in the United States. This clinical study will be conducted as a multicenter, open-label study of EN3835 in adult women with EFP. The study will consist of 3 treatment visits, 21 days apart. Subjects meeting the entry criteria for this study will receive EN3835 treatment within an investigational site and assigned region (ie, bilateral buttocks or bilateral thighs) on Day 1, Day 22, and Day 43, and will be followed for up to 180 days from the first day of treatment. Subjects will receive follow-up visits at 1, 3, 6, and 13 days after each treatment course (either by phone or, for subjects participating in the photographic sub-study, in the clinic), and 2 follow-up visits at Day 90 and Day 180 to assess treatment effectiveness. The study also includes a photographic sub-study (conducted at two sites) in which subjects will return to the clinic for photographs at 1, 3, 6, and 13 days after each treatment course to coincide with the follow up visits. Sites participating in the photographic sub-study will also follow subjects for the same 180-day period.

The complete schedule of events is provided in section 5.

Figure 1: Study Design

[figure not shown]

Table 3: Study Treatment Groups

Dose per Each Injection ^a / Number of Subjects	Injection Volume per Each Injection	Number of Injections at Each Treatment Visit	Dose (mg) at Each Treatment Visit	Injection Volume (mL) per Each Treatment Visit	Cumulative EFP Dose
EN3835 0.07 mg/ N=up to 150	0.3 mL	12 per treatment area x 2 treatment areas = 24	0.84 mg per treatment area x 2 treatment areas = 1.68 mg (12 injections per treatment area x 0.07 mg/injection x 2 treatment areas)	3.6 mL per treatment area x 2 treatment areas = 7.2 mL (24 injections x 0.3 mL)	5.04 mg (3 treatment visits x 0.84 mg per treatment area x 2 treatment areas)

^a Each injection of study drug is 0.3 mL administered as three 0.1 mL aliquots.

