3.1.3.2. Study Drug Administration

A dose of 0.84 mg of EN3835 per treatment area will be administered as 12 subcutaneous injections (0.3-mL injection administered as three 0.1-mL aliquots per injection) in each of two treatment areas for a total dose of 1.68 mg and a total volume of 7.2 mL (3.6 mL per treatment area). Total number of injections will be 24 injections per treatment visit into the assigned region (left and right buttocks or left and right posterolateral thighs). There will be 3 treatment visits at 21-day intervals, ie, treatments on Days 1, 22, and 43 will be administered.

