3.4.7.1. Adverse Events

The following listings will be provided based on all AEs:

- Listing of AEs
- Listing of deaths
- Listing of SAEs
- Listing of AEs leading to discontinuation

The following summary tables of AEs will be presented by assigned region (buttock or thigh) and overall:

- Treatment-Emergent AEs
 - Overall summary
 - By preferred term

- By preferred term and severity
- By frequency for SAEs
- By frequency for most common non-serious AEs
- Treatment-Related AEs
 - Overall summary
 - By preferred term
 - By preferred term and severity
 - By preferred term and treatment session
 - Duration of AEs

The overall summary will consist of the following items:

- Total number of AEs
 - All AEs
 - Mild AEs
 - Moderate AEs
 - Severe AEs
- Total number of subjects with
 - At least one AE
 - At least one SAE
 - At least one severe AE
 - At least one AE leading to discontinuation
- Total number of subjects who died (Treatment-emergent only)

Percentages for the total number of mild, moderate, and severe AEs will be based on the total number of all AEs in the corresponding assigned region and overall.

The by frequency summaries will also include the total number of occurrences the AE preferred term was reported as well the number of subjects with at least one report of the AE. Most common non-serious AEs are any preferred term AE that at least 5% of the subjects report at least once.

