- Table by preferred term and treatment session – If an AE preferred term occurred multiple times with a body system for the same subject within a treatment session, the preferred term will only be counted once for the subject in the treatment session for the summary of preferred terms. If an AE preferred term occurred multiple times within a body system for the same subject in different treatment sessions, the preferred term will be counted at each treatment session. If an AE body system occurred multiple times for the same subject within a treatment session, the body system will only be counted once for the subject in the treatment session for the summary of body systems. If an AE body system occurred multiple times for the same subject in different treatment sessions, the body system will be counted at each treatment session for the summary of body systems. If a subject has any AE within a treatment session, the subject will be counted once in the treatment session in the summary of subjects with at least one AE. If a subject has any AE in different treatment sessions, the subject will be counted in each treatment session in the summary of subjects with at least one AE.
- Table by duration of treated-related TEAE and treatment session – For each subject within each treatment session, every event will have its duration calculated. The multiple events for the same SOC and the same PT will be combined together for the sum of duration. Therefore for each SOC/PT in each treatment session, each subject will only have at most one (sum) duration which will be classified into one of the duration categories (≥ 1 to ≤ 4 days, > 4 to ≤ 7 days, > 7 to ≤ 14 days, ≥ 15 to ≤ 21 days, and >21 days).
- For ongoing AEs, the category of AE duration will be missing unless those events have an onset date 21 days prior to the subject's last visit in the study. In this case, the category of the AE duration will be classified as " > 21 days".
- Table of frequency of preferred terms – Preferred terms will be ordered by their descending frequency in the overall safety population. If 2 or more preferred terms are tied in their frequency, then the preferred terms will be ordered alphabetically.

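### The by-session AE tables set a 138-day Session 3 beside two 21-day sessions, so late-onset or recurrent terms can look more frequent or longer-lasting in Session 3

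*SAP*

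**What the plan says.** SAP 3.2.6.1.1 assigns each AE to a session by its start date:

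- Session 1: "Adverse events with a start date between the Day 1 visit date and the day prior to the Day 22 visit date".
- Session 2: "AEs with a start date between the Day 22 visit date and the day prior to the Day 43 visit date".
- Session 3: "AEs with a start date between the Day 43 visit date and the Day 180 (EOS/ET) visit date".

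SAP Table 8 repeats the open end: an AE belongs to the treatment session before its onset, with no upper limit on the time since injection.

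Two outputs use this split. Under treatment-related AEs, SAP 3.4.7.1 lists a table "By preferred term and treatment session", and SAP 3.4.7.1.1 counts a subject once per term per session. SAP 3.4.7.1.1 also describes a duration table by session, in which "The multiple events for the same SOC and the same PT will be combined together for the sum of duration". SAP 3.2.6.1.2 defines duration as end date minus start date plus 1. It also says that duration is worked out session by session, but not whether an event that runs past the next injection is cut there.

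Neither document gives a common post-injection window, a person-time adjustment or a late-onset row for these tables. The by-session denominator is not stated.

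**The concern.** The three columns will be read side by side, but they do not cover the same length of time after injection. A term that can start weeks after an injection, or come and go, has much longer to be counted in Session 3. Repeat events of that term also have longer to be added into one duration.

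Safety is the primary objective. Protocol 10.3 notes that the product is a foreign protein, and Protocol 8.1.3 reports that all treated subjects were seropositive after three treatment visits in earlier work. Whether reactions change with repeat injection is therefore a real question. Among the AE tables listed in SAP 3.4.7.1, these are the only ones split by session. For late or recurrent terms, a rise at Session 3 could reflect only the longer window, and a true fall with repeat dosing could be hidden by it.

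**Working it through.** **1. Window lengths.** The plan states "There will be 3 treatment visits at 21-day intervals, ie, treatments on Days 1, 22, and 43 will be administered". The visit days reproduce the interval: 22 − 1 = 21 and 43 − 22 = 21, which are also the nominal lengths of Sessions 1 and 2. Session 3 is 180 − 43 + 1 = 138 days, and 138/21 = 6.57.

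The Schedule of Events allows ±3 days at Days 22 and 43 and +7 days at Day 180:

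- Session 1: 19 − 1 = 18 to 25 − 1 = 24 days.
- Session 2: 40 − 25 = 15 to 46 − 19 = 27 days.
- Session 3: 180 − 46 + 1 = 135 to 187 − 40 + 1 = 148 days.

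**2. A conflict that governs the 138.** Protocol 14.5.1 ends AE collection 28 days after the last dose. With a last dose on Day 43 that is Day 71, so Session 3 would be 71 − 43 + 1 = 29 days, and 29/21 = 1.38. The Schedule of Events, Protocol 12.6 and 12.7 and SAP 3.2.6.1.1 all carry AEs to Day 180.

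**3. Incidence.** Let *a* be the proportion with an acute reaction soon after injection, *p* the proportion with onset from a constant background per 21 days, and *L* the window length. Cumulative incidence is 1 − (1 − a)(1 − p)^(L/21). The documents give neither *a* nor *p*, so the values below are assumptions. The 75% is close to the 75.1% for bruising in Protocol 8.3.

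| a | p | 21 days | 29 days | 138 days |
|---|---|---|---|---|
| 0 | 1% | 1.0% | 1.4% | 6.4% |
| 0 | 5% | 5.0% | 6.8% | 28.6% |
| 75% | 1% | 75.3% | 75.3% | 76.6% |
| 75% | 5% | 76.3% | 76.7% | 82.2% |

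With *p* = 0 all sessions are equal. The rate per day at risk does not rise in any row; only cumulative incidence does.

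**4. Durations.** A simulation gave every session the same true durations (lognormal, median 7 days, log-SD 0.8) and 60% acute incidence. All of these are assumptions.

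| Scenario (Sessions 1 / 2 / 3) | Mean days | Over 21 days |
|---|---|---|
| Acute only, uncut | 9.65 / 9.65 / 9.62 | 8.0 / 8.1 / 8.0% |
| Plus 5% background of the same term, uncut | 10.1 / 10.1 / 12.2 | 9.2 / 9.2 / 14.8% |
| Acute only, cut at session boundary | 8.61 / 8.61 / 9.66 | 0 / 0 / 8.1% |

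Uncut, the longest single event observable by Day 180 is 180 days from Day 1, 159 from Day 22 and 138 from Day 43, so Session 3 has the least room. The uncut excess comes from summing repeat events. With a cut, a single event in Session 1 or 2 cannot nominally exceed 21 days.

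**5. Contacts.** Protocol 10.1 says "Subjects will receive follow-up visits at 1, 3, 6, and 13 days after each treatment course", the same in every session, and then "2 follow-up visits at Day 90 and Day 180 to assess treatment effectiveness". After post-injection day 13, Sessions 1 and 2 have a gap of 21 − 13 = 8 days to the next visit. Session 3 has 90 − 56 = 34 days and then 180 − 90 = 90 days. Density differs only after about Day 56.

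**The case against.** The strongest reply is that the tables hold treatment-related AEs only. Protocol 8.4 describes the drug's activity as local and nearly finished within a day, and Protocol 10.2 says most earlier AEs were at the injection site and gone before the next treatment. Such onsets fall well inside 21 days in every session, so the dominant terms barely move (75.3% against 76.6%). This stands, and it makes the constant-onset figures an upper-end illustration. It does not remove the point: SAP 3.2.6.1 counts possibly related AEs, and AEs with no recorded relationship, as treatment-related, so the table is not confined to acute reactions.

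A reader might infer that Session 3 rates and durations must be higher by construction, and that the change in contact density adds to this. The documents do not support that. Rates per day need not rise, and uncut single-event durations are not longer. Contacts are identical to day 13 after each injection, and sparser contact later would tend to lower AE capture, which works the other way.

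The tables are also descriptive, with no test between sessions. Onset day is derived for each AE, and SAP 3.5.5.1 has listings show, when applicable, days from the start of the treatment session. A careful reader could separate early from late onsets from the listings. That softens the consequence but leaves the summary tables not like for like.

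**Conclusion.** The point holds in a limited form. On nominal days Session 3 is 6.57 times as long as Session 1 or 2, with no common window or person-time. Its cumulative incidence, and durations summed over repeat same-term events, can be inflated for late-onset or recurrent terms. The effect is near zero for acute injection-site terms. At a constant onset of 1% per 21 days it reaches 6.4%, or about 1.4% if AE collection stops 28 days after the last dose. Sparser contact after about Day 56 may offset part of it, so the net size is uncertain. Single-event durations are affected only if the SAP means to cut them at the session boundary, which it leaves unclear. All projected percentages and durations rest on assumed onset rates and durations; the window lengths come from the documents' own visit days. The change is a worthwhile, low-cost improvement.

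**What to change.** In SAP 3.2.6.1.1 and 3.4.7.1.1:

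- Build the by-session incidence and duration tables on onsets from the injection date to 20 days after it, or to the day before the next injection if that is earlier. For Session 3 this is nominally Days 43 to 63.
- Show later onsets in a separate late-onset column. After the third injection this covers Days 64 to 180, or 180 − 64 + 1 = 117 days.
- Sum durations only over events with onset inside the window, and state that each duration runs uncut from start to end.
- Leave the full-study TEAE tables as they are.

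Separately, reconcile the AE collection period in Protocol 14.5.1 with the Schedule of Events, Protocol 12.6 and 12.7 and SAP 3.2.6.1.1. The nominal common window closes on Day 63, before both Day 71 and Day 180, so its columns stand under either reading.

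The cost is SAP wording, one flag derived from dates already collected, and one extra column. Limits remain. Late reactions to injections 1 and 2 still fall in the next session, Session 2 windows can be as short as 15 days, and Session 3 still has no visit at the end of its window (the next is Day 90).
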